3.1.1. Considerations Regarding COVID-19

May 11, 2023, marked the end of the COVID-19 public health emergency (PHE) declaration in the US. The CDC states that many people in the United States now have some protection or immunity against COVID-19 due to vaccination, previous infection, or both. This immunity, combined with the availability of tests and treatments, has greatly reduced the risk of severe illness, hospitalization, and death from COVID-19 for many people (<https://www.cdc.gov/coronavirus/2019-ncov/your-health/covid-by-county.html>).

At the same time, some people—such as those who are older, are immunocompromised, have certain disabilities, or have certain underlying health conditions—continue to be at higher risk for serious illness. Mitigating risks of infections, including from endemic COVID-19, in immunocompromised populations remains important.

Participants are strongly recommended to be up to date with COVID-19 vaccinations per current CDC recommendations at the time of screening with last vaccine at least 14 days prior to Visit 1 (Day 0).

3.2. Primary Endpoint

The primary endpoint is the change in percentage of UVB-induced apoptotic epidermal cells from Visit 2 (Day 1) (pre-treatment) to Visit 5 (Day 26) (post-treatment). Percentage of UVB-induced apoptotic cells at a visit is defined as the difference between the percentage of apoptotic epidermal cells in the UVB-exposed biopsy and percentage of apoptotic epidermal cells in the unexposed biopsy at the same visit. More information can be found in Section 8.5.5, *Research Assessments*.

3.3. Secondary Endpoints

1. Change in MED due to UVB from Visit 2 (Day 1) to Visit 5 (Day 26)

2. Change in UVB-induced expression of inflammatory genes in skin from Visit 2 (Day 1) to Visit 5 (Day 26), based on enumeration of RNA transcripts. UVB-induced expression is defined as the difference in expression measured in the biopsy exposed at the Visit 2 (Day 1) 1x MED and that measured in the unexposed biopsy
3. Change in Cutaneous Lupus Erythematosus Disease Area and Severity Index (CLASI) activity score from Visit 1 (Day 0) to Visit 4 (Day 25)
4. Change in CLASI damage score from Visit 1 (Day 0) to Visit 4 (Day 25)
5. Change in Systemic Lupus Erythematosus Disease Activity Index 2000 (SLEDAI-2K) total score from Visit 1 (Day 0) to Visit 4 (Day 25)
6. Changes in laboratory parameters
7. Incidence of adverse events

3.4. Stratification, Randomization, and Blinding/Masking

This is a single-arm open-label study. There are no plans for stratification, randomization, or masking.

4. Selection of Participants

4.1. Study Population

This study can fulfill its objectives only if appropriate participants are enrolled. The following eligibility criteria are designed to select participants for whom the study is considered appropriate. All relevant medical and nonmedical conditions should be taken into consideration when deciding whether a particular participant is suitable for this protocol. For this Phase 1 study, conditions indicative of serious disease, such as CNS lupus or lupus nephritis, are excluded by limiting the total SLEDAI-2K score for clinical manifestations to ≤ 4 at entry.

4.2. Inclusion Criteria

Individuals must meet all of the following inclusion criteria to be eligible for enrollment in the study:

1. Cutaneous lupus erythematosus based upon all of the following:
 - a. a clinical diagnosis made by a rheumatologist or dermatologist of one of the following: acute cutaneous lupus erythematosus, subacute cutaneous lupus, or chronic cutaneous lupus erythematosus;
 - b. active skin disease within 5 years prior to screening.Participants may have concomitant SLE.
2. SLEDAI-2K score ≤ 4 (clinical criteria only, excludes all laboratory criteria) for all participants regardless of whether they have concomitant SLE.
3. If taking oral corticosteroids, the dose must be ≤ 10 mg daily of prednisone (or equivalent), stable dose for at least 4 weeks, and not anticipated to change over the course of the study.
4. If taking oral anti-malarial medications, the dose(s) must be ≤ 100 mg daily for quinacrine or/and ≤ 400 mg daily for hydroxychloroquine, stable for at least 6 months, and not anticipated to change over the course of the study.
5. If taking oral or subcutaneous methotrexate, the dose must be ≤ 25 mg weekly, stable for at least 4 weeks, and not anticipated to change over the course of the study.
6. If taking oral leflunomide, the dose must be ≤ 20 mg daily, stable for at least 4 weeks, and not anticipated to change over the course of the study.
7. If taking oral mycophenolate mofetil (MMF) or mycophenolic acid, the dose must be equivalent to ≤ 3000 mg of MMF daily, stable for at least 4 weeks, and not anticipated to change over the course of the study.
8. Adults 18 to 65 years of age at screening.

9. All participants and/or their sexual partners who engage in sexual activity that could lead to pregnancy must be willing to use complete abstinence or an FDA-regulated form of contraception for the duration of the study and for at least one month after discontinuation of study drug to prevent pregnancy. Highly effective birth control methods include, but are not limited to, hormonal contraception, an intrauterine device, or surgical options. Periodic abstinence and withdrawal are not acceptable methods of birth control.

4.3. Exclusion Criteria

Individuals who meet any of these criteria are not eligible for enrollment as study participants:

1. Inability or unwillingness of a participant to give written informed consent or comply with study protocol.
2. Current or recent history, within the last year, of uncontrolled clinically significant renal, hepatic, hematologic, gastrointestinal, metabolic, endocrine, pulmonary, cardiac, or neurologic disease or significant impairment that might negatively impact the participant's ability to participate or that may put a participant at increased risk.
3. Potential active nephritis and/or urinary tract infection at screening, defined as any one of the following determined at screening unless otherwise specified:
 - a. >10 RBCs /hpf,
 - b. >5 WBCs /hpf with either positive nitrites or greater than a trace leukocyte esterase,
 - c. Signs or symptoms of a urinary tract infection,
 - d. For individuals with no history of nephritis: Urine protein (mg/dL): creatinine (mg/dL) ratio (Pr/Cr)>0.5 at screening or a Pr/Cr level that has exceeded 1.0 in the prior 12 months,
 - e. For individuals with a history of nephritis: A rise in Pr/Cr of >0.5 over the prior 3-6 months prior to screening.
4. History of severe gastrointestinal narrowing or strictures.
5. Medically confirmed history of diverticulitis or chronic, ulcerative lower gastrointestinal (GI) disease such as Crohn's disease, ulcerative colitis, or other symptomatic, lower GI conditions that might predispose a participant to perforations.
6. History of thrombosis, pulmonary embolism, or antiphospholipid syndrome.
7. History of any one of the following anti-phospholipid antibodies:
 - a. Positive lupus anticoagulant test, or
 - b. Anti-β2-glycoprotein I IgG ELISA titer \geq 40 GPL, or
 - c. Anti-cardiolipin IgG ELISA titer \geq 40 GPL.
8. History of chronic pulmonary disease requiring supplemental oxygen including chronic obstructive pulmonary disease (COPD) requiring chronic treatment, interstitial lung disease (ILD) requiring immunosuppressive therapy, and asthma requiring chronic steroid (other than inhaled steroid) or biologic therapy.
9. History of moderate to severe atherosclerotic cardiovascular disease as evidenced by prior coronary artery bypass surgery, coronary artery stent placement, myocardial infarction, symptomatic carotid arterial disease, peripheral vascular disease, abdominal aortic aneurysm; or angina within the past 8 weeks prior to Visit 1 (Day 0).
10. History of keloid scarring.
11. History of any lymphoproliferative disorder or other malignancy with the exception of successfully treated or excised basal cell or squamous cell skin cancer or cervical cancer in situ.
12. Other autoimmune diseases likely to require immunosuppression.
13. Any of the following lab results at screening:
 - a. Hemoglobin <9.5 g/dL
 - b. White Blood Cell count $<3.5 \times 10^9$ /L

- c. Absolute Neutrophil count $<1.2 \times 10^9/L$
- d. Platelet count $<120 \times 10^9/L$
- e. Absolute Lymphocyte count $<0.75 \times 10^9/L$
- f. Alanine Aminotransferase (ALT) or Aspartate Aminotransferase (AST) $> 1.5 \times$ the upper limit of normal (ULN)
- g. Total bilirubin $>$ ULN
- h. Estimated glomerular filtration rate [GFR] $<60mL/min/1.73 m^2$
- i. Triglycerides $\geq 300 \text{ mg/dL}$ (fasting not required)
- j. Total Cholesterol $\geq 240 \text{ mg/dL}$ (fasting not required).

14. Major surgery $<$ 8 weeks prior to Visit 1 (Day 0).

15. Hospitalized for serious infection $<$ 4 weeks prior to Visit 1 (Day 0).

16. Chronic infections other than chronic or intermittent uncomplicated urinary tract infections (including but not limited to tuberculosis (TB), chronic pyelonephritis, osteomyelitis).

17. Presumed or documented COVID-19 infection within 30 days prior to Visit 1 (Day 0).

18. Recent (within one month prior to screening) close contact with a person who has active TB infection.

19. History of untreated active or latent TB infection.

20. History of incompletely treated active or latent TB infection unless at least one month of treatment has been completed prior to screening.

21. Positive Interferon-Gamma Release Assay (IGRA) or positive purified protein derivative tuberculin skin test (PPD) ($> 5\text{mm}$ induration) at screening.

22. An indeterminate IGRA at screening unless followed by a subsequent negative IGRA or negative PPD.

23. History of human immunodeficiency virus (HIV).

24. A positive test for HIV antigen/antibody or nucleic acid test (NAT) at screening.

25. History of a hepatitis B infection.

26. A positive test for hepatitis B surface antigen or hepatitis B core antibody at screening.

27. History of a hepatitis C infection.

28. A positive test for hepatitis C antibody (regardless of whether hepatitis C RNA levels are undetectable) at screening.

29. History of recurrent (more than one episode) herpes zoster, one or more episodes of any of the following: herpes zoster ophthalmicus, or disseminated herpes zoster, or disseminated herpes simplex.

30. Current, recent ($<$ 4 weeks prior to Visit 1 (Day 0)) or chronic use of antibiotic medication, except for suppression of chronic/recurrent urinary tract infection, which is allowed.

31. Simultaneous use of more than one of the following: leflunomide, methotrexate and MMF.

32. Any of the following active medications (oral or parenteral): cyclosporine, voclosporin, cyclophosphamide, tacrolimus, rituximab or other anti-CD20s, or any other investigational or marketed biologic with immunomodulatory properties within a year prior to Visit 1 (Day 0).

33. Any of the following medications (oral or parenteral): azathioprine or belimumab within 3 months prior to Visit 1 (Day 0).

34. Any prior treatment with cell-depleting therapies other than anti-CD20s including but not limited to CAMPATH, anti-CD4, anti-CD5, anti-CD3, anti-CD19 products.

35. Intravenous or intramuscular corticosteroids within 2 weeks prior to Visit 1 (Day 0).

36. Treatment with any investigational agent \leq 4 weeks or \leq 5 half-lives of the investigational drug prior to Visit 1 (Day 0), whichever is longer.

37. Treatment with more than one dose of ketoconazole within one week of screening.

38. Any prior treatment with chlorambucil, bone marrow transplantation, or total lymphoid irradiation.
39. Vaccinated or exposed by close contact, e.g., within a household, to a live/attenuated vaccine \leq 6 weeks prior to Visit 1 (Day 0); or is expected to be vaccinated or to have household exposure to these vaccines during treatment or during the 6 weeks following discontinuation of study medication.
40. Received a non-live vaccine \leq 2 weeks prior to initiation of study drug, or unwillingness of a participant to delay non-live vaccination until 1 month after completion of study therapy.
41. Pregnant or breastfeeding females.
42. History of alcohol or substance abuse, unless in full remission for greater than 6 months prior to first dose of study drug.
43. Past or current medical or psychiatric conditions or findings from physical examination or laboratory testing that are not listed above, which, in the opinion of the investigator, may pose additional risks from participation in the study, may interfere with the participant's ability to comply with study requirements or that may impact the quality or interpretation of the data obtained from the study.

5. Known and Potential Risks and Benefits to Participants

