- Strong CYP3A4 inhibitors increase exposure to tofacitinib. Participants taking ketoconazole are excluded from this study.

2. Co-administration with biologic DMARDs or potent immunosuppressive drugs such as azathioprine or cyclosporine is not recommended.

3. Pregnancy, Lactation, and Reproductive potential:

- Available data in pregnant women are insufficient to establish a drug associated risk of major birth defects, miscarriage or adverse maternal or fetal outcomes. Feticidal and teratogenic effects were noted in animal reproduction studies.

- There are no data on the presence of tofacitinib in human milk, the effects on a breastfed infant, or the effects on milk production. Tofacitinib is present in the milk of lactating rats; it is likely that the drug will be present in human milk.
- Pregnancy planning and prevention is recommended for females of reproductive potential and is planned for this study.

4. **Vaccinations:** Avoid use of live vaccines concurrently with tofacitinib. The interval between live vaccinations and initiation of tofacitinib therapy should be in accordance with current vaccination guidelines regarding immunosuppressive agents.

5. **Hepatic impairment:** Tofacitinib has not been studied in individuals with severe hepatic impairment and its use is not recommended. In studies of individuals with moderate hepatic impairment, tofacitinib blood concentration is higher than individuals with normal hepatic function. Higher blood concentrations may increase the risk of some adverse reactions. In addition, the safety and efficacy of tofacitinib have not been studied in patients with positive hepatitis B virus or hepatitis C virus serology.

6. **Renal impairment:** In individuals with moderate or severe renal impairment, tofacitinib blood concentrations are higher than in individuals with normal renal function.

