6.4. Toxicity Prevention and Management

Prevention

- Entry criteria and laboratory testing are designed to exclude individuals with identifiable risk factors.
- Participants will be informed of the need to be up-to-date with respect to vaccinations per current immunization guidelines. They will be asked to confirm their vaccination status with their provider before enrolling in this study. Vaccination of participants with live components is prohibited within the 6 weeks prior to Visit 1 (Day 0), during treatment, or during the 6 weeks following discontinuation of study medication. Non-live vaccines should be administered at least 2 weeks prior to initiation of study drug and should not be administered during treatment or during the one month after completion of study drug.
- Concurrent use of drugs that are contradicted with tofacitinib 11 mg per day is prohibited while on study treatment (See Section 7.3, *Prohibited Medications*).
- Safety monitoring will serve to monitor for adverse events that require further evaluation and/or treatment.

Management

- Participants will be seen in clinic on Day 14, approximately 2 weeks after starting study drug, to evaluate signs and symptoms and screen for possible adverse events.
- Participants will be instructed to call the study coordinator if signs or symptoms of an infection occur during the course of the study.

- Prior to biopsies, participants will be asked about allergies to local anesthetics and solutions used to prepare the biopsy site. A stitch will be used to close the skin biopsy site to minimize the risk of infection and scar formation. Biopsies will be performed using sterile techniques by trained staff, and participants will be provided with wound care instructions to minimize the risk of infection.

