7.3. Prohibited Medications

Use of tofacitinib in combination with biologic DMARDs or potent immunosuppressants not listed in Section 7.1.2, such as azathioprine, voclosporin, and cyclosporine is not allowed. Oral corticosteroids, other than specified in Section 7.1.2, and parenteral corticosteroids are prohibited. Methotrexate, leflunomide, or MMF may be continued at stable doses indicated in Section 7.1.2, but they may not be used simultaneously with each other.

No topical therapies of any kind can be used on the area exposed to UVB from the time of the UVB exposure assessment until the skin biopsy has been taken the next day. Chemical sunscreens should not be used on the region that will be exposed to UVB for at least 12 hours prior to the UVB exposure assessment. Zinc and titanium-based sunscreens may be used, but will need to be removed prior to UVB treatment.

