8.5.2. General Assessments

- **Informed Consent**
- **Demographics:** Participants should provide demographic information. In particular, race and ethnicity should be self-identified.
- **Medical History:** Medical history will be performed as part of screening activities and standard medical care. The medical history assessment will include current illnesses/conditions and past medical history.
- **Concomitant Medications:** A current list of prescription and over-the-counter medications, supplements, and treatments for CLE and SLE will be obtained. Assessment of eligibility should include a review of permitted and prohibited medications. The medication, dose, frequency, route, start date, stop date, and indication will be captured in the electronic case report form (eCRF). Medications taken 30 days prior to screening through study completion or termination should be reported.
- **Eligibility Review:** All entry criteria should be reviewed, and eligibility confirmed prior to scheduling Visit 1 (Day 0) and again at Visit 1 (Day 0) before drawing blood or phototesting (UVB exposure).

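### Section 5.1 excludes participants taking ketoconazole, but exclusion 37 looks only around screening and the prohibited list in 7.3 does not name the drug

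*Combined protocol and SAP*

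**What the plan says.** Section 5.1 states both the reason and the intention, with no time limit: "Strong CYP3A4 inhibitors increase exposure to tofacitinib. Participants taking ketoconazole are excluded from this study". Exclusion 37, worded identically in the synopsis and section 4.3, is the only entry criterion that acts on this: "Treatment with more than one dose of ketoconazole within one week of screening". It tolerates a single dose and says nothing about use after entry.

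For the treatment period, section 6.4 says: "Concurrent use of drugs that are contradicted with tofacitinib 11 mg per day is prohibited while on study treatment". It then refers to section 7.3 for the list. Section 7.3 covers biologic DMARDs, potent immunosuppressants, corticosteroids beyond the permitted ones, combined use of methotrexate, leflunomide or MMF, and topical products or sunscreens on the test area. It names neither ketoconazole nor CYP3A4 inhibitors. Section 8.5.2 makes that list part of the entry check: "Assessment of eligibility should include a review of permitted and prohibited medications".

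**The concern.** The sponsor has already decided that people taking ketoconazole should not be in this study. That decision is in the risk section. The two rules a site would work from, the entry criterion and the prohibited list, do not reliably enforce it. A site following item 37 to the letter could enrol someone who began ketoconazole after the screening visit. A site consulting 7.3 during treatment would find no entry for the drug.

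At stake are participant safety and uniform exposure in a study of 10 completers. There is also a consequence for the analysis sets in section 13.4.1. PP1, used for the primary analysis, is defined by having both sets of phototests and biopsies, so co-administration would not remove anyone from it. Only PP2 screens out deviations that could affect photosensitivity. Whether taking ketoconazole counts as such a deviation currently depends on how 6.4 is read.

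**Working it through.** The plan gives no figure on this point to reproduce, and nothing here enters the sample size, the significance level or the test. The check sets the texts side by side and adds day counts.

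**1. Anchors of the timed drug and vaccine exclusions (section 4.3)**

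- Items 30, 32, 33, 35, 36 and 39 count back from Visit 1. Item 35 is typical: "Intravenous or intramuscular corticosteroids within 2 weeks prior to Visit 1 (Day 0".
- Item 40 counts back from initiation of study drug.
- Item 37 counts from screening.

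That is 6 + 1 = 7 of 8 anchored to Visit 1 or study-drug start, with item 37 the exception. Items 39 and 40 also look forward into treatment and beyond. Item 37 does not.

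**2. The interval before Visit 1 that item 37 does not reach**

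Inputs: screening runs from Day -30 to Day -1 and Visit 1 is Day 0 (Table 8.1); the first dose is on Day 2 (section 3.1). Let s be the day of a single screening visit, from -30 to -1.

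- *Week before a single visit.* The window closes on day s. Gap to Visit 1 = 0 - s, which is 1 to 30 days.
- *A week either side of a single visit.* The window closes on day s + 7. Gap = max(0, -s - 7). For s = -30 this is 23 days; for s = -7 or later it is 0. Range 0 to 23 days.
- *Whole screening period.* The window runs to Day -1, so there is no practical gap at Visit 1.

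From a single screening visit to the first dose is 2 - s, or 3 to 32 days. The gap concerns ketoconazole newly started after the window closes. Someone who stopped before screening has a longer washout, not a shorter one.

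Section 8.5.2 has all criteria reviewed again at Visit 1. That review applies item 37 as worded, so it does not move the anchor.

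**3. The on-treatment rule**

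Section 5.1 raises two drug-combination concerns, and they are handled differently.

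- Immunosuppressants. Section 5.1: "Co-administration with biologic DMARDs or potent immunosuppressive drugs such as azathioprine or cyclosporine is not recommended". Section 7.3 carries this over by name: "potent immunosuppressants not listed in Section 7.1.2, such as azathioprine, voclosporin, and cyclosporine is not allowed".
- CYP3A4 inhibition. Section 5.1 singles out ketoconazole. Section 7.3 has no counterpart.

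The cross-reference in 6.4 therefore leads to a list without the drug. Dosing runs from Day 2 to Day 26, 26 - 2 + 1 = 25 doses, and no on-treatment rule names ketoconazole. Starting it is not among the suspension reasons in 6.5.2. Table 8.2 schedules no clinical blood draw between screening and Visit 4 (Day 25), so laboratory effects of raised exposure would not routinely be seen before then.

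**The case against.** The strongest reply is that the documents describe screening as a period. Table 8.1 gives a range of days and section 8.2 a 30-day window; neither defines a single screening visit. On that reading the entry gap vanishes. This stands as far as it goes: the gap of up to 30 days depends on the single-visit reading, which is an assumption. It does not touch the omission from 7.3.

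A second reply is that screening anchors are common in the full list, for example items 3, 18 and 20. That is true. The contrast holds only among drug and vaccine exclusions. It shows inconsistent drafting, not that an ineligible person has been or would be admitted.

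Third, safeguards exist. Section 5.1 has no time limit and 6.4 has a general ban. Medications are reviewed at every visit. Item 16 excludes chronic infections, item 43 allows investigator judgement, and 6.5.2 suspends dosing for any infection of grade 2 or higher. These make the event unlikely, but none is an explicit rule on ketoconazole. Item 30 covers antibiotics and does not name antifungals. After a short suspension, 6.6 lets dosing resume without the entry-criteria recheck that it requires for a new course.

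A reader might also infer that at a Restart Visit item 37 still points back to the original screening date, leaving a gap of many weeks. The documents do not support that. Section 6.6 requires all entry criteria to be met again, and footnote H of Table 8.2 has the laboratory tests repeated for that purpose. Those include tests behind items 3 and 13, which are themselves worded in terms of screening. The Restart Visit is thus treated as a fresh assessment.

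**Conclusion.** The concern holds as a minor correction for participant safety and consistent exposure. Two things are established from the text: item 37 is the one timed drug or vaccine exclusion of eight that is not anchored to Visit 1 or study-drug start, and the list that 6.4 relies on omits the drug that 5.1 singles out. The size of the entry gap depends on the reading: 1 to 30 days, 0 to 23 days, or none in practice. The omission from 7.3 does not depend on that reading.

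Two stronger conclusions might be drawn and should not be. The protocol does not permit ketoconazole during treatment; 5.1 and 6.4 together imply a bar, and the fault is that it is left to inference. Nor can a bias in the primary result be claimed. The documents give neither the size of the exposure increase nor the frequency of ketoconazole use, which is probably low, so no effect on the primary test can be quantified.

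**What to change.** Reword item 37, in both the synopsis and section 4.3, so that it counts back from Visit 1 or the start of study drug. Add ketoconazole by name to section 7.3 as prohibited from the first through the last dose of tofacitinib, stating that this covers delayed and restarted courses. The reference from 6.4 and the medication review in 8.5.2 then lead to an explicit rule, and co-administration becomes a clear deviation to weigh for PP2. Section 5.1 speaks of strong CYP3A4 inhibitors as a class; whether to name others is for the sponsor to decide from the prescribing information.

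The cost is amended wording in three places. No new data are needed, because concomitant medications are already recorded at every visit. The downside is an occasional deferred participant.
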